8.3 Study Treatment & Day of Discharge from Hospital

Activities related to Days 2-29 or until discharge are listed in **Table 13**. At each daily visit, the Daily eCRF must be completed.

Table 13. Days 2-29 or until discharge daily activities.

Assessment	Information
SoC concomitant medication & supportive treatment assessment	
 Taken as prescribed and recorded daily, as above for Day 1. Any new infection occurring during participation, regardless of organism (i.e. viral or non-viral), should be captured. Additionally, the site of infection and source of culture (e.g., BAL, tracheal aspirate, sputum, blood, urine etc.) should be recorded.
SoC laboratory results	
 Routine laboratory and imaging tests performed as recommended by the treating physician (Section 8.1.4 and Appendix 3).
Clinical status assessment (7-point ordinal scale)	
 Assessed and documented daily, as above for Day 1.
Vital sign assessment	
 Assessed and documented daily, as above for Day 1.
Blinded study medication dispensing & collection	
 Blinded study medication dispensed and collected by study staff on Days 12 and 24 and discharge. Dispensing and collection data is documented.
Blinded study medication dosing	
 Taken daily, as above for Day 1. On the Day of Discharge, study medication may be dosed as deemed appropriate by Investigator. Document date and time taken.
Adverse Events assessments	
 Assessed and recorded daily, as above for Day 1.

8.4 Discharge Activities

For the Day of Discharge (Day 29 or the last day in the hospital if discharged before Day 29), the Daily eCRF will be completed as above (**Table 13**) as well as a Discharge eCRF to document how the patient was discharged (**Table 14**).

Table 14. Day of discharge activities.

Assessment	Information
Record discharge information	
 • Discharged (yes/no).* • If discharged, the Date of discharge and reason (e.g., COVID-19 negative, recovered, not discharged [remains hospitalized] etc.) is noted. Date of scheduled follow-up telephone call. • Where the patient was discharged to (e.g., home, rehab center, etc.). • If the patient was COVID-19 positive or negative at discharge (yes/no/unknown). • Which medications the patient was discharged with. • If supplemental oxygen was prescribed for treatment after discharge.

* Patients not discharged from the hospital by Day 29

Some study patients may not be ready for discharge from the hospital by Day 29. In these instances, study treatment and data collection procedures still end on Day 29 (with the exception of contacts in the next section). This information will be noted in the Discharge eCRF as “study treatment complete, but patient remains hospitalized.” This would also be captured in the Day 29 Clinical status assessment (7-point ordinal scale).

Patients that remain hospitalized after Day 29 will be contacted as described in the next section.

8.5 Post Discharge/Day 29 Contacts

Following Day 29 or discharge from the hospital (if earlier), there will be three points of contact with all study patients, regardless of hospitalization status. Each contact will require the completion of a Follow-up eCRF (**Table 15**).

- Discharge Contact: 4 to 10 days after discharge from hospital, if discharged within the 29-day treatment period.
 - If the patient remains hospitalized after Day 29, study treatment and data collection procedures still end on Day 29 (with the exception of contacts in this section) and contact with the patient will take place 4 to 10 days after receipt of last dose of study medication (Day 29).
- Day 29 Contact: 26 to 32 days after first dose of study medication. If the Discharge Contact and Day 29 Contact fall within same window, this contact will be combined to the Day 29.

- Day 60 Follow-up: 55 to 65 days after first dose of study medication.
 - Should a patient or their medical contact be unable to be contacted at any of these timepoints, a vital records search will be performed to determine the patient’s vital status approximately 60 days after first dose of study medication.

Table 15. Post-discharge follow-up activities.

Assessment	Information
Follow-up date	
 • Date of follow-up contact
Clinical status assessment (7-point ordinal scale)	
 • Assessed and documented, as above for Day 1 (clinical and vital status)
Re-hospitalization status or remains in hospital	
 • Any incidence of re-admission to the hospital following a 24-hour period of discharge (date and duration) that is related to COVID-19 • Date of discharge (if after Day 29) should be noted in the Follow-up eCRF.
Adverse Events assessments	
 • Documented, as above for Day 1

8.6 Adverse Events

The definitions of an AE or SAE can be found in [Appendix 4](#). The SoA is Table 3 in [Section 1.3](#).

Adverse events will be reported by the patient and/or investigator and recorded on the AE CRF.

The Investigator and any designees are responsible for detecting, documenting, and recording events that meet the definition of an AE or SAE and remain responsible for following up AEs that are serious, considered related to the study medication or study procedures, or that caused the patient to discontinue the study ([Appendix 4](#)).

As stated in [Section 8.6](#), medical condition(s) identified during the screening visit will be documented as medical history and not as an adverse event(s) unless the condition worsens during the trial and meets the definition of an adverse event.

8.6.1 Time period and frequency for collecting AE and SAE information

For this study, AEs and SAEs will be collected from the time of the first dose of study medication through the follow-up (end of study) visit.

SAEs assessed as related to study participation (e.g., study treatment, protocol-mandated procedures, invasive tests or change in existing therapy) will be collected from the time of consent through the follow-up visit.

All SAEs will be recorded and reported to the Sponsor or designee within 24 hours, as indicated in [Appendix 4](#). The Investigator will submit any updated SAE data to the Sponsor designee within 24 hours of it being available.

Investigators are not obligated to actively seek AE or SAE after conclusion of the study participation. However, if the Investigator learns of any SAE, including a death, at any time after a patient has been discharged from the study, and he/she considers the event to be reasonably related to the study medication or study participation, the Investigator must promptly notify the Sponsor.

The method of recording, evaluating, and assessing causality of AE and SAE and the procedures for completing and transmitting SAE reports are provided in [Appendix 4](#).

8.6.2 Method of detecting AEs and SAEs

Care will be taken not to introduce bias when detecting AEs and/or SAEs. Open-ended and non-leading verbal questioning of the patient is the preferred method to inquire about AE occurrences.

8.6.3 Follow-up of AEs and SAEs

After the initial AE/SAE report, the Investigator is required to proactively follow each patient at subsequent visits/contacts. All SAEs, will be followed until resolution, stabilization, the event is otherwise explained, through the follow-up visit, or the patient is lost to follow-up (as defined in [Section 7.3](#)). Further information on follow-up of AEs and SAEs are given in [Appendix 4](#).

8.6.4 Regulatory reporting requirements for SAEs

- Prompt notification by the Investigator to the Sponsor of an SAE is essential so that legal obligations and ethical responsibilities towards the safety of patients and the safety of a study medication under clinical investigation are met. The Investigator will submit any updated SAE data to the Sponsor designee within 24 hours of it being available.
- The Sponsor has a legal responsibility to notify both the local regulatory authority and other regulatory agencies about the safety of a study medication under clinical investigation. The Sponsor will comply with country-specific regulatory requirements relating to safety reporting to the regulatory authority, Institutional Review Boards (IRB)/Independent Ethics Committees (IEC), and Investigators.
- Investigator safety reports must be prepared for suspected unexpected serious adverse reactions (SUSAR) according to local regulatory requirements and Sponsor policy and forwarded to Investigators, as necessary.
- An Investigator who receives an Investigator safety report describing an SAE or other specific safety information (e.g. summary or listing of SAEs) from the Sponsor will review and then file it along with the Investigator's Brochure and will notify the IRB/IEC, if appropriate according to local requirements.

8.6.5 Pregnancy

- Details of all pregnancies in female patients will be collected after the start of study medication and until 30 days after the last dose of study medication.

- If a pregnancy is reported, the Investigator should inform the Sponsor within 24 hours of learning of the pregnancy and should follow the procedures outlined in [Appendix 5](#).
- Abnormal pregnancy outcomes (e.g. spontaneous abortion, fetal death, stillbirth, congenital anomalies, ectopic pregnancy) are considered SAEs.

8.6.6 Adverse Events of special interest

Adverse events of special interest have not been identified for ensifentrine.

8.7 Treatment of Overdose

An overdose is defined as a dose greater than the total daily doses prescribed in this study which results in clinical signs and symptoms. These should be recorded by the investigator on the AE/SAE pages.

In the event of an overdose the investigator should use clinical judgement in treating the overdose and contact the study medical monitor. Verona Pharma is not recommending specific treatment guidance for overdose and toxicity management.

9 PROTOCOL EXEMPTIONS/WAIVERS

The investigator should not implement any deviation from, or changes of, the protocol without agreement by the sponsor and prior review and documented approval/favorable opinion from the IRB/IEC of an amendment, except where necessary to eliminate an immediate hazard(s) to trial subjects, or when the change(s) involves only logistical or administrative aspects of the trial (e.g., change in monitor(s), change of telephone number(s)).

- The investigator, or person designated by the investigator, should document and explain any deviation from the approved protocol.
- The investigator may implement a deviation from, or a change in, the protocol to eliminate an immediate hazard(s) to trial subjects without prior IRB/IEC approval/favorable opinion. As soon as possible, the implemented deviation or change, the reasons for it, and, if appropriate, the proposed protocol amendment(s) should be submitted:
 - (a) To the IRB/IEC for review and approval/favorable opinion;
 - (b) To the sponsor for agreement and, if required;
 - (c) To the regulatory authority(ies)

Regulatory, ethical and study oversight details are included in [Appendix 2](#).

10 STATISTICAL CONSIDERATIONS

10.1 Statistical Hypotheses

All analyses are considered exploratory and hypothesis-generating. All tests will be two-sided at 5% significance level. Hypothesis tested for the primary endpoint will be if addition of ensifentrine to SoC for up to 29 days could increase the proportion of patients with recovery versus standard of care plus placebo. The status according to the 7-point ordinal scale of all patients regardless of treatment withdrawal will be followed up during the scheduled treatment period (Day 29) and at a follow-up Day 60, or as far as possible. Secondary endpoints are tested independently and there will be no adjustment for multiple tests.

Study days for analyses include Day 1 (start dose), Day 7 (6 to 8 days after 1st dose), Day 14 (13 to 15 days after 1st dose) and Day 29.

10.2 Study Populations

Modified intent to treat (mITT):

- Will consist of all randomized and treated patients. Efficacy will be evaluated as randomized.

Per protocol population (PP):

- Will consist of all patients in mITT without any major protocol deviations deemed to have an effect on efficacy analyses.

Safety set (SS):

- Will consist of all randomized and treated patients. Safety will be evaluated by actual treatment.

10.3 Sample Size Determination

This is a pilot study and it is not powered based on any specific endpoint. Sample size has been set to minimize the number of patients exposed, but still large enough to give reliable estimates on the efficacy and safety of ensifentrine in the target population.

10.4 Efficacy

The proportion of patients with recovery at Day 29 will be compared between treatment groups using a logistic regression model adjusting for treatment. The treatment difference will be expressed as an odds ratio with 95% confidence intervals and associated two-sided p-value. Potential stratification variables such as age group and/or gender may be considered depending on the randomization outcome, details will be given in the Statistical Analysis Plan.

The time to recovery from Day 1 to Day 29 will be compared between treatment groups using a log-rank test; patients not in recovery at end-of study/withdrawal will be censored at last observed time point in the treatment period or at last time status was assessed if collected post treatment-withdrawal. Patients with death as outcome will be censored at the scheduled end-of-study day 29. Data will be illustrated using Kaplan-Meier plots and

the median time to recovery estimated if appropriate. Stratification in the model with respect to age group and/or gender may be considered based on the randomization outcome.

Secondary endpoints of survival type will be compared between treatments using the log rank test similar to the time to recovery endpoint. Secondary endpoints assessing proportion of patients fulfilling an event will be compared between treatments using a logistic regression. Continuous outcomes will be compared between treatments using ANCOVA models with treatment and stratification groups as factors and baseline as a covariate. Estimated treatment difference with 95% confidence intervals and associated 2-sided p-value will be given. Endpoints assessing duration of (days with) additional oxygen use/ventilator need will be compared between treatments using Wilcoxon rank sum test.

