
Number of Patients

Approximately 45 randomized patients are planned.

Treatment Groups and Duration

Every patient enrolled will receive UAB's SoC treatment for COVID-19 infection.

Upon enrollment, patients will be randomized 2:1 to receive blinded ensifentrine via pMDI BID + SoC or placebo pMDI BID + SoC over 29 days or until discharge from hospital, whichever is first.

- Treatment Arm 1 (n=30): Blinded ensifentrine (2 mg) pMDI BID + Standard of Care treatment for COVID-19 infection
- Treatment Arm 2 (n=15): Blinded placebo pMDI BID + Standard of Care treatment for COVID-19 infection

Statistical Methods

[figure not shown]
All analyses are considered exploratory and hypothesis-generating.

Sample Size

This is a pilot study and it is not formally powered based on any specific endpoint. Sample size has been set to minimize the number of patients exposed, but still large enough to give reliable estimates on the efficacy and safety of ensifentrine in the target population.

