6 INVESTIGATIONAL PLAN

6.1 Overall Study Design and Plan

The purpose of this study is to evaluate the effect of ensifentrine on the proportion of patients hospitalized with COVID-19 infection with recovery over 29 days.

This is a single center, randomized, double-blind, parallel group, placebo-controlled study to determine the efficacy and safety of ensifentrine 2 mg BID administered via pMDI added on to SoC treatment for COVID-19 infection compared to patients receiving SoC plus placebo.

Patients 18 to 80 years of age must be hospitalized with a confirmed diagnosis of SARS-CoV-2 infection confirmed by PCR test and displays at least one of the following: Respiratory rate greater than 24, new cough, new atypical chest pain, new dyspnea, oxygen saturation <97% at rest, chest x-ray with new changes consistent with COVID-19 related airspace disease.

Patients meeting criteria for inclusion and none of the criteria for exclusion at randomization will be randomized to receive study medication within 4 days of hospital admission until hospital discharge or up to 29 days of treatment, whichever comes first. Patients will be randomized 2:1 to receive one of the following study treatments:

- Treatment Arm 1 (n=30): Blinded ensifentrine (2 mg) pMDI BID + Standard of Care treatment for COVID-19 infection
- Treatment Arm 2 (n=15): Blinded placebo pMDI BID + Standard of Care treatment for COVID-19 infection

Randomized patients will receive blinded ensifentrine or placebo twice daily, approximately 12 hours apart in the morning and evening, through 29 days or until discharge from hospital, whichever is first. Patients will self-administer 4 actuations (puffs) pMDI observed by study staff at each dosing event.

During the treatment period, patients will undergo all assessments and procedures as outlined in the schedule of activities until hospital discharge. Patients completing treatment will complete a study contact (telephone or visit as required) within 4 to 10 days of discharge or early withdrawal. All enrolled patients will complete a telephone contact 26 to 32 days (Day 29) and 55-65 days (Day 60) following receipt of 1st dose of study medication for assessment of clinical status via the 7-point ordinal scale, need for re-hospitalization and vital status.

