8 GENERAL STATISTICAL CONSIDERATIONS

8.1 Sample Size

This is a pilot study and it is not powered based on any specific endpoint. Sample size has been set to minimize the number of patients exposed, but still large enough to give reliable estimates on the efficacy and safety of ensifentrine in the target population.

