8.2 General Principles

This is a double-blind, placebo controlled randomized pilot study which may inform on treatment effect for future studies.

All analyses are considered exploratory and hypothesis-generating. All tests will be two-sided at 5% significance level. Hypothesis tested for the primary endpoint will be if addition of ensifentrine to SoC for up to 29 days could increase the proportion of patients with recovery versus standard of care plus placebo. The status according to the 7-point ordinal scale of all patients regardless of treatment withdrawal will be followed up during the scheduled treatment period (Day 29) and at a follow-up Day 60, or as far as possible.

Secondary endpoints are tested independently and there will be no adjustment for multiple tests.

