9.4.2.1 Sub-sets based on post-randomization outcome

Descriptive summaries of the proportion of patients as well as the duration of the worsening following initiation of study medication will be provided for these endpoints:

- Proportion of patients needing re-hospitalization (post-dose Day 1 Day 60).
 - Applies to the sub-set of patients that were randomized, treated with study medication and discharged from the hospital alive then re-admitted to the hospital for COVID-19 related treatment.
- Proportion of patients and duration of new oxygen use (post-dose Day 1 Day 29; measured in days).
 - Applies to the sub-set of patients that were randomized and treated with study medication but then had a new need for supplemental oxygen (score worsened to 4, 5 or 6).
 - Or those which improved during hospitalization (to 3) and then their clinical status worsened again (to 4, 5 or 6).
- Proportion of patients and duration of new non-invasive ventilation or high flow oxygen use (post-dose Day 1 - Day 29; measured in days).
 - Applies to the sub-set of alive patients that were randomized and treated with study medication but then had a new need for non-invasive ventilation or highflow oxygen use (score worsened to 5 or 6).
 - Or those which improved during hospitalization (to 3 or 4) and then their clinical status worsened again (to 5 or 6)

The total number of days with recorded use will be the sum of all reported days, regardless of whether the days occur consecutively or in disjoint intervals.

9.4.3 Change from baseline in 7-point ordinal scale (Days 7, 14 and 29).

Change from baseline in 7-point ordinal scale will be compared between treatments using ANCOVA models with treatment and COVID disease severity state as factors and baseline as a covariate. Estimated treatment difference with 95% confidence intervals and associated 2-sided p-value will be given. Sub-group analysis will only be performed for sub-groups with a minimum size.

9.4.4 Total time on supplemental oxygen (Day 1 - Day 29; measured in days).

The total number of days with recorded use will be the sum of all reported days, regardless of whether the days occur consecutively or in disjoint intervals. Results will be summarized by descriptive statistics including medians and quartiles by treatment arm and compared between treatment groups using Wilcoxon rank sum test. Patients that do not reach the specified score on any day will be counted as 0 days.

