Day 1 - Day 29	n		
-	Yes		
	No		

pg. 54 Confidential

⁽or discharge, whichever was first)
*7-point ordinal scale score = 1, 2, 3, 4 or 5. n = number of patients with recorded value

Table 14.2.11: Summary of Proportion of patients re-hospitalized following initiation of study medication and subsequent discharge (over 60 days), ITT

Proportion of Patients	Re-hospitalized	Enrolled (N=45)	Ensifentrine (N=30)	Placebo (N=15)
Day 1 - Day 60	ay 1 - Day 60 n			
	Yes			
	No			

n = number of patients with recorded value

Table 14.2.12: Duration of hospitalization from initiation of study medication (Day 1 - Day 29 (or discharge, whichever was first); measured in days), ITT

Days of hospitalization	Enrolled		Placebo p-value*
from Day 1	(N=45	(N=30)	(N=15)
Median (Q1 - Q3)			

^{*}Wilcoxon rank sum test

Hospitalized = # days where the 7-point ordinal scale score = 3, 4, 5 or 6.

Discharge = The patient is discharged and leaves the hospital alive.

pg. 56 Confidential

Table 14.2.13: Change from Baseline in 7-point Ordinal Scale at Days 7, 14, and 29, ITT

Change from 7-point Ordin	n Baseline in nal Scale	Enrolled (N=45)	Ensifentrine (N=30)	Placebo (N=15)
Day 7	n Mean (SD)	()	()	()
Day 14	n Mean (SD)			
Day 29	n Mean (SD)			

Computed from Day 1 scale minus Day 7, Day 14, and Day 29 scale accordingly (or discharge) (or discharge, whichever was first)

pg. 57 Confidential

Table 14.2.14: Total time on Supplemental Oxygen (Day 1 - Day 29; measured in days), ITT

Days of Suppl	emental Oxygen	Enrolled	Ensifentrine	Placebo
(Scale=4)		(N=45)	(N=30)	(N=15)
Day 1 - 29	Median (Q1 - Q3)			

Hospitalized patient: 7-point ordinal scale score = 4, 5, or 6. Or 7-point ordinal scale score is equal to 7 if patient dies while hospitalized between Day 1-29.

Not hospitalized patient supplemental oxygen = # days where the 7-point ordinal scale score is equal to 2 (if required to have home oxygen).

pg. 58 Confidential

Table 14.2.15: Total time of non-invasive ventilation or high flow oxygen use (post-dose Day 1 - Day 29 (or discharge, whichever was first); measured in days)

Days of non-invasive ventilation or High Flow Oxygen Use (Scale=5)		Enrolled (N=45)	l Ensifentrine (N=30)	Placebo (N=15)
Day 1 - 29	Median (Q1 - Q3)			

Non-invasive ventilation or high flow oxygen use = # days where the 7-point ordinal scale score is equal to 5 or 6. Or 7-point ordinal scale score is equal to 7 if patient dies while hospitalized between Day 1-29.

pg. 59 Confidential

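### Four secondary endpoints (time to recovery; days on oxygen, on NIV/high-flow and in hospital) get a test and by-arm summaries but no between-arm effect estimate or confidence interval

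*Protocol*

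**What the plan says.** The protocol's sentence on duration endpoints (10.4) is "Endpoints assessing duration of (days with) additional oxygen use/ventilator need will be compared between treatments using Wilcoxon rank sum test". It covers oxygen and ventilator days. Hospital days are not named there and could fall under that section's rule for continuous outcomes, which is ANCOVA with a difference and 95% interval.

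The SAP assigns all three day counts to the rank test. Section 9.4.4 (oxygen) states: "Results will be summarized by descriptive statistics including medians and quartiles by treatment arm and compared between treatment groups using Wilcoxon rank sum test". Sections 9.4.5 (NIV) and 9.4.6 (hospital) repeat that sentence.

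For time to recovery, protocol 10.4 and SAP 9.4.1 plan a log-rank test, Kaplan-Meier plots and a median if appropriate.

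The example shells follow the same pattern:
- 14.2.5 (time to recovery) has mean, median and the log-rank p-value.
- 14.2.12 (hospital days) has median, quartiles and a p-value.
- 14.2.14 (oxygen) and 14.2.15, whose row label begins "Days of non-invasive ventilation or High Flow Oxygen Use (Scale=5", have median and quartiles only.

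Other endpoints are treated differently. SAP 9.3 and 9.4.2 give a difference in proportions with a delta-method interval (raw proportions only if a group has no events), and 9.4.3 gives an ANCOVA difference with a 95% interval. SAP 8.2 describes the study as one "which may inform on treatment effect for future studies".

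**The concern.** A pilot passes on effect sizes and their uncertainty. SAP 8.1 says plainly "This is a pilot study and it is not powered based on any specific endpoint", and 8.2 sets every test at the two-sided 5% level. For an endpoint reported as a p-value and two medians, a non-significant result cannot show whether the data rule out a useful effect, a harmful one, or neither. These four endpoints carry much of the secondary objectives on time to recovery, hospitalization, ventilation and oxygen use.

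NIV/high-flow days have a further problem. A patient who never reaches the score counts as 0 days, so if fewer than half of each arm escalates, the medians are 0 and 0 whatever the treatment does to the patients who do escalate.

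**Working it through.** The documents state no power, effect size, recovery count or NIV rate, so there is no planned figure to reproduce. The only given arithmetic is 45 patients split 2:1, that is 30 and 15. Rates and event counts below are assumptions.

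**Time to recovery.** With d recoveries and 2:1 allocation, SE(log ratio) = 1/√(d × 2/3 × 1/3). The 95% interval is the estimate divided and multiplied by exp(1.96 × SE). Power is Φ(ln(ratio)/SE − 1.96). The upper value of d, 45, means that every patient recovers.

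| Recoveries | SE | Interval factor | Power at 1.5 | Power at 2 | Interval if 1.5 is observed |
|---|---|---|---|---|---|
| 30 | 1/√6.67 = 0.387 | 2.14 | 18.1% | 43.2% | 0.70 to 3.20 |
| 45 | 1/√10 = 0.316 | 1.86 | 24.9% | 59.2% | 0.81 to 2.79 |

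An observed ratio of 1.5 would be non-significant in either row, yet its interval reaches about 3. The planned output would not show that.

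**NIV/high-flow days.** Shells 14.1.5a and 14.1.5b show 1 enrolled patient at score 3 and 44 at score 4. Since 1 + 44 = 45, nobody starts at score 5. Both medians are 0 if at most 14 of 30 and at most 7 of 15 patients ever reach score 5, 6 or 7. Both upper quartiles are also 0 if at most 7 of 30 and at most 3 of 15 do. Exact binomial probabilities, with the same rate in both arms:

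| Share ever at score 5 or worse | Both medians 0 | Both upper quartiles also 0 |
|---|---|---|
| 10% | >99.9% | 93.7% |
| 20% | 99.6% | 49.3% |
| 30% | 93.4% | 8.4% |
| 40% | 64.9% | 0.4% |
| 50% | 21.4% | 0.0% |

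**Which estimates would work.** These come from simulation, 4,000 trials of 30 v 15 per setting.
- Oxygen days (lognormal, medians 4 v 5, log-scale SD 0.7, capped at 29): the Hodges-Lehmann shift averages about −1.0 day, with an average 95% interval of about −3.1 to +1.0. It is informative here.
- NIV days (10% v 20% ever affected, 1 to 14 days each): the Hodges-Lehmann shift is exactly 0 in 99.7% of trials, so it adds nothing. The mean difference averages −0.7 day, and 95% of trials fall between −2.9 and +1.0.
- A percentile-bootstrap 95% interval for the difference in mean NIV days, checked in a separate simulation, covers the truth in only about 76% (5% v 10% escalating), 90% (10% v 20%) and 92% (15% v 30%) of trials. At a 10% placebo rate, 0.9^15 = 21% of trials have no placebo patient with any NIV day, so that arm contributes no variance.

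**The case against.** The strongest reply is that much of this information is planned elsewhere, and most of that reply stands.
- Recovery is compared as a proportion, with a difference and interval, at Days 7, 14, 29 and 60. Oxygen use and non-invasive ventilation are compared in the same way at Days 7, 14 and 29. A reader might infer that the pilot produces no estimate or interval at all; SAP 9.3, 9.4.2 and 9.4.3 show otherwise.
- Time to recovery is not reduced to a p-value, because curves and a median are planned.
- SAP 9.4.2.1 promises a descriptive summary of how many patients newly need NIV/high-flow, and for how long. With nobody at score 5 at baseline, that is essentially all such use.
- The shells are labelled as examples and leave out things that the SAP text requires: 14.2.13 lacks the ANCOVA interval, and 14.2.14 and 14.2.15 lack the Wilcoxon p-value. SAP section 12 allows extra output, and the day-count wording does not exclude means. The case therefore rests on the SAP text, with the shells only as support.
- Low power is no defect in a study declared unpowered and exploratory.

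What remains is that fixed-day differences do not summarize time to recovery or total days, 9.4.2.1 is descriptive only, and permission to add output is not a plan to report an effect.

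**Conclusion.** The point holds for these four secondary endpoints and no further. Neither document plans an effect measure or interval for time to recovery, oxygen days or NIV/high-flow days, and the SAP plans none for hospital days. That falls short of what the SAP does for its other endpoints and of its stated purpose.

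The size is moderate. With 30 to 45 recoveries, the log-rank test would miss a true ratio of 2 in about 41% to 57% of trials (100 − 59.2 and 100 − 43.2), and of 1.5 in about 75% to 82%.

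A reader might expect NIV days to print 0 v 0 for certain. The documents do not support that, since they give no escalation rate. It is very probable below about 30% and unlikely at 50%, and upper quartiles may exceed 0. The protocol sentence also should not be read as covering hospital days or time to recovery; the sources for those are SAP 9.4.6 and 9.4.1.

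This is worth changing, but it does not threaten the primary analysis.

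**What to change.** Keep every planned test, and add:

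(a) In SAP 9.4.1 and shell 14.2.5, the recovery rate ratio from a Cox model with a 95% interval, using the censoring already planned (deaths at Day 29) so that it matches the log-rank test. The difference in restricted mean days to Day 29 is optional.

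(b) In 9.4.4 and 9.4.6 and shells 14.2.14 and 14.2.12, a between-arm difference in days with a 95% interval, either Hodges-Lehmann or a mean difference, named in advance.

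(c) In 9.4.5 and shell 14.2.15, mean days per patient by arm with zeros included, and the difference in the proportion ever on NIV/high-flow or worse with a small-sample (score or exact-type) 95% interval. Present these beside the days among users from 9.4.2.1. Do not rely on a percentile bootstrap for mean NIV days, because it under-covers when few patients escalate.

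The cost is SAP wording, a few shell columns and some programming, with no new data. The intervals will be wide, exploratory and unadjusted, and should be labelled so.
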